10.4.4 Planned Interim Analysis

Data will be reviewed by the Investigator and Study Chair before advancing to the next cohort, but formal interim analyses will not be performed.

11. SAFETY REPORTING AND ANALYSES

Safety assessments will consist of monitoring and recording protocol-defined AEs and SAEs, measurement of protocol-specified hematology, clinical chemistry, and urinalysis variables, measurement of protocol-specified vital signs, and other protocol-specified tests that are deemed critical to the safety evaluation of the study drug.

The Principal Investigator is responsible for recognizing and reporting AEs to the SCRI Innovations Safety Department (see Section 11.1.7). It is the Sponsor's responsibility to report relevant SAEs to the applicable local, national, or international regulatory bodies. In addition, Investigators must report SAEs and follow-up information to their responsible IRB according to the policies of that IRB.

CONFIDENTIAL

STUDY DRUG: MLN9708
FINAL PROTOCOL: 11 APRIL 2014
AMENDMENT NUMBER 3: 11 FEBRUARY 2016

SCRI INNOVATIONS STUDY NUMBER: MM 42

VERSION 4

The Principal Investigator is also responsible for ensuring that every staff member involved in the study is familiar with the content of this section.

11.1 Definitions

11.1.1 Pretreatment Event Definition

A pretreatment event is any untoward medical occurrence in a patient or subject who has signed informed consent to participate in a study but before administration of any study medication; it does not necessarily have to have a causal relationship with study participation.

11.1.2 Adverse Events

Adverse event means any untoward medical occurrence associated with the use of a drug in humans, whether or not considered drug related. An AE (also known as adverse experience) can be any unfavorable and unintended sign (e.g., an abnormal laboratory finding), symptom, or disease temporarily associated with the use of a drug, without any judgement about causality. This includes any newly occurring event, or a previous condition that has increased in severity or frequency since the administration of study drug. An AE can arise with any use of the drug (e.g., off-label use, use in combination with another drug) and with any route of administration, formulation, dose or including overdose.

An abnormal laboratory value will not be assessed as an AE unless that value leads to discontinuation or delay in treatment, dose modification, therapeutic intervention, or is considered by the investigator to be a clinically significant change from baseline.

11.1.3 Serious Adverse Event

An AE or a suspected adverse reaction is considered “serious” if it results in any of the following outcomes:

- **Death**
- **A life-threatening AE (refers to an AE in which the patient was at risk of death at the time of the event. It does not refer to an event which hypothetically might have caused death if it were more severe)**
- **Inpatient hospitalization of at least 24-hours or prolongation of existing hospitalization**
- **A persistent or significant incapacity or substantial disruption of the ability to conduct normal life functions**
- **A congenital anomaly/birth defect**

Important medical events that may not result in death, be life-threatening, or require hospitalization may be considered serious when, based upon appropriate medical judgment, they may jeopardize the patient or subject and may require medical or surgical intervention to prevent one of the outcomes listed in this definition. Examples of such medical events include allergic bronchospasm requiring intensive treatment in an emergency room or at home, blood dyscrasias or convulsions that do not result in hospitalization, or development of drug dependency or drug

CONFIDENTIAL

STUDY DRUG: MLN9708
FINAL PROTOCOL: 11 APRIL 2014
AMENDMENT NUMBER 3: 11 FEBRUARY 2016

SCRI INNOVATIONS STUDY NUMBER: MM 42

VERSION 4

abuse; any organism, virus, or infectious particle (eg, prion protein transmitting Transmissible Spongiform Encephalopathy), pathogenic or nonpathogenic, is considered an infectious agent.

It is important to distinguish between “serious” and “severe” AE, as the terms are not synonymous. Severity is a measure of intensity; however, an AE of severe intensity need not necessarily be considered serious. Seriousness serves as the guide for defining regulatory reporting obligations. “Serious” is a regulatory definition and is based on patient/event outcome or action usually associated with events that pose a threat to a patient’s life or vital functions. For example, nausea which persists for several hours may be considered severe nausea, but may not be considered an SAE. On the other hand, a stroke which results in only a limited degree of disability may be considered only a mild stroke, but would be considered an SAE. Severity and seriousness should be independently assessed when recording AEs on the eCRF and SAEs on the SAE Report Form.

11.1.4 Adverse Event of Special Interest Definition

Adverse Events of Special Interest (AESIs) are a subset of AEs that are to be reported to Millennium on a quarterly basis by the sponsor-investigator. Millennium will provide the current list of AESIs and updates to the list will be distributed to the sponsor-investigator as appropriate.

11.1.5 Adverse Reaction

An adverse reaction means any AE caused by a drug. Adverse reactions are a subset of all suspected adverse reactions where there is a reason to conclude that the drug caused the event.

11.1.6 Suspected Adverse Reaction

Suspected adverse reaction means any AE for which there is a reasonable possibility that the drug caused the AE. Reasonable possibility means that there is evidence to suggest a causal relationship between the drug and the AE. A suspected adverse reaction implies a lesser degree of certainty about causality than adverse reaction, which means any adverse event caused by a drug.

11.1.7 Recording and Reporting of Adverse Events

Recording of Adverse Events

All AEs of any patient during the course of the research study will be recorded in the eCRF, and the Investigator will give his or her opinion as to the relationship of the AE to the study drug treatment (i.e., whether the event is related or unrelated to study drug administration).

All AEs should be documented. A description of the event, including its date of onset and resolution, whether it constitutes an SAE or not, any action taken (e.g., changes to study treatment), and outcome, should be provided, along with the Investigator’s assessment of causality (i.e., the relationship to the study treatment[s]). For an AE to be a suspected treatment-related event there should be at least a reasonable possibility of a causal relationship between the protocol treatment and the AE. Adverse events will be graded according to the NCI CTCAE v4.0, and changes will be documented.

If the AE is serious, it should be reported immediately to SCRI Innovations Safety Department. Other untoward events occurring in the framework of a clinical study are to be recorded as AEs

CONFIDENTIAL

STUDY DRUG: MLN9708

SCRI INNOVATIONS STUDY NUMBER: MM 42

FINAL PROTOCOL: 11 APRIL 2014

AMENDMENT NUMBER 3: 11 FEBRUARY 2016

VERSION 4

(i.e., AEs that occur prior to assignment of study treatment that are related to a protocol-mandated intervention, including invasive procedures such as biopsies, medication washout, or no treatment run-in).

Any clinically significant signs and symptoms; abnormal test findings; changes in physical examination; hypersensitivity; and other measurements that occur will be reported as an AE, and collected on the relevant eCRF screen.

Test findings will be reported as an AE if: the test result requires an adjustment in the study drug(s) or discontinuation of treatment, and/ or test findings require additional testing or surgical intervention, a test result or finding is associated with accompanying symptoms, or a test result is considered to be an AE by the Investigator.

Reporting Period for Adverse Events

All AEs regardless of seriousness or relationship to MLN9708 treatment (called study treatment), spanning from the start of study treatment, until 30 calendar days after discontinuation or completion of study treatment as defined by the clinical study for that patient, are to be recorded on the corresponding screen(s) included in the eCRF.

All AEs resulting in discontinuation from the study should be followed until resolution or stabilization. All new AEs occurring during this period must be reported and followed until resolution unless, in the opinion of the Investigator, the AE or laboratory abnormality/ies are not likely to improve because of the underlying disease. In this case, the Investigators must record his or her reasoning for this decision in the patient's medical record and as a comment on the eCRF screen.

After 30 days of completion of protocol-specific treatment or discontinuation, only AEs, SAEs, or deaths assessed by the Investigator as treatment related are to be reported.

11.1.8 Assessment of Adverse Events

All AEs and SAEs whether volunteered by the patient, discovered by study personnel during questioning, or detected through physical examination, laboratory test, or other means will be reported appropriately. Each reported AE or SAE will be described by its duration (i.e., start and end dates), regulatory seriousness criteria if applicable, suspected relationship to the study drug (see following guidance), and actions taken. For serious pretreatment events, the investigator must determine both the intensity of the event and the relationship of the event to study procedures.

To ensure consistency of AE and SAE causality assessments, Investigators should apply the following general guideline:

YES: There is a plausible temporal relationship between the onset of the AE and administration of the study medication, and the AE cannot be readily explained by the patient's clinical state, intercurrent illness, or concomitant therapies, and/or the AE follows a known pattern of response to the study drug, and/or the AE abates or resolves upon discontinuation of the study drug or dose reduction and, if applicable, reappears upon re-challenge.

CONFIDENTIAL

STUDY DRUG: MLN9708
FINAL PROTOCOL: 11 APRIL 2014
AMENDMENT NUMBER 3: 11 FEBRUARY 2016

SCRI INNOVATIONS STUDY NUMBER: MM 42

VERSION 4

NO: Evidence exists that the AE has an etiology other than the study drug (e.g., pre-existing medical condition, underlying disease, intercurrent illness, or concomitant medication), and/or the AE has no plausible temporal relationship to study drug administration (e.g., cancer diagnosed 2 days after first dose of study drug).

11.2 Serious Adverse Event Reporting by Investigators

Adverse events classified by the treating Investigator as serious require expeditious handling and reporting to SCRI Innovations Safety Department in order to comply with regulatory requirements. Determination of life-threatening or serious is based on the opinion of either the Sponsor or the Investigator.

Serious AEs may occur at any time from the start of study treatment through 30 days after the last dose of study drug. **The SCRI Innovations Safety Department must be notified of all SAEs, regardless of causality, within 24 hours of the first knowledge of the event by the treating physician or research personnel.**

To report a SAE, the SAE Report Form should be completed with the necessary information.

The SAE report should be sent to SCRI Innovations Safety Department via fax or e-mail using the following contact information (during both business and non-business hours):

SCRI Innovations Safety Department

Safety Dept. [contact]

Safety Dept. Email: [contact]

Transmission of the SAE report should be confirmed by the site personnel submitting the report.

Follow-up information for SAEs and information on non-serious AEs that become serious should also be reported to SCRI Innovations Safety Department as soon as it is available; these reports should be submitted using the SCRI Innovations SAE Report Form.

Investigators must report SAEs and follow-up information to their responsible IRB according to the policies of the responsible IRB.

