7. STUDY ASSESSMENTS AND EVALUATIONS

7.1 Overview

All patients should visit the study center on the days specified within this protocol. The complete Schedule of Assessments for this study is shown in Appendix D.

Informed consent must be obtained ≤ 28 days prior to initiation of treatment and before any protocol-specific procedures are performed. The Baseline visit physical examination including vital signs, medical history, ECOG performance status, complete blood counts (CBC), differential and platelets, comprehensive metabolic profile (CMP), urinalysis, and PT/aPTT/INR should be done ≤ 7 days prior to initiation of treatment. However, if these initial examinations are obtained within 72 hours of first study drug administration they do not have to be repeated on

CONFIDENTIAL

STUDY DRUG: MLN9708
FINAL PROTOCOL: 11 APRIL 2014
AMENDMENT NUMBER 3: 11 FEBRUARY 2016

SCRI INNOVATIONS STUDY NUMBER: MM 42

VERSION 4

Day 1 of Cycle 1. A pregnancy test must be performed within 72 hours of first study drug administration.

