11.4 Sponsor Serious Adverse Event Reporting Requirements

AEs which are serious must be reported to Millennium Pharmacovigilance (or designee) from the date the participant signs Informed Consent through 30 days after administration of the last dose of MLN9708. Any SAE that occurs at any time after completion of MLN9708 treatment or after the designated follow-up period that the sponsor-investigator and/or sub-investigator considers to be related to any study drug must be reported to Millennium Pharmacovigilance (or designee). In addition, new primary malignancies that occur during the follow-up periods must be reported, regardless of causality to study regimen, for a minimum of three years after the last dose of the investigational product, starting from the first dose of study drug. All new cases of primary malignancy must be reported to Millennium Pharmacovigilance (or designee).

Planned hospital admissions or surgical procedures for an illness or disease that existed before the patient was enrolled in the trial are not to be considered AEs unless the condition deteriorated in an unexpected manner during the trial (e.g., surgery was performed earlier or later than planned). All SAEs should be monitored until they are resolved or are clearly determined to be due to a patient's stable or chronic condition or intercurrent illness(es).

Since this is an investigator-initiated study, SCRI Innovations Safety Department on behalf of the sponsor-investigator, is responsible for reporting serious adverse events (SAEs) to any regulatory agency and to the sponsor- investigator's EC or IRB.

Follow-up information on the SAE may be requested by Millennium. The SAE report must include event term(s), serious criteria, and the sponsor-investigator's or sub-investigator's determination of both the intensity of the event(s) and the relationship of the event(s) to study drug administration. Intensity for each SAE, including any lab abnormalities, will be determined by using the NCI CTCAE version used at your institution, as a guideline, whenever possible. The criteria are available online at <http://ctep.cancer.gov/reporting/ctc.html>.

SCRI Innovations Safety Department will forward SAE information to Millennium Pharmaceuticals, Inc., within 1 business day of SCRI Innovations Safety Department personnel becoming aware of the SAE.

CONFIDENTIAL

STUDY DRUG: MLN9708
FINAL PROTOCOL: 11 APRIL 2014
AMENDMENT NUMBER 3: 11 FEBRUARY 2016

SCRI INNOVATIONS STUDY NUMBER: MM 42

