- ^m Bone marrow aspirate and biopsy – quantify percent myeloma cell involvement, and obtain bone marrow aspirate for cytogenetics [i.e., diploidy, del(13)] and FISH studies [i.e., t(4:14); t(11:14);del(17p)], and at the response assessments to confirm CR only. If available, provide MRD by flow cytometry at baseline.
- ⁿ Skeletal survey (lateral radiograph of the skull, anteroposterior and lateral views of the spine, and anteroposterior views of the pelvis, ribs, femora, and humeri) ≤ 28 days of first study drug treatment. Only repeat if clinically indicated (i.e., bone pain).
- ^o UPEP requires the collection of a 24-hour urine sample.
- ^p Repeat if abnormal at baseline.
- ^q All patients will undergo the end of treatment visit assessments listed within 30 days after treatment ends due to completion of the planned study treatment period, or once a patient is discontinued due to unacceptable toxicity or decision to discontinue treatment by the patient or the study physician. If treatment is discontinued because of toxicity or any other reason(s) at a treatment visit and no study treatment is administered, that visit may fulfill the End of Treatment Visit. After withdrawal from or completion of protocol treatment, patients must be followed for AEs for 30 calendar days after the last dose of study drug.
- ^r Patients who discontinue study treatment prior to the occurrence of disease progression will be followed every 3 months during years 1 and 2.
- ^s After disease progression is documented, patients will be followed every 3 months during years 1 and 2 for survival assessment.
- ^t For known plasmacytomas, utilize the same modality used to assess original disease (i.e., PET, MRI, CT, etc).
-

CONFIDENTIAL

STUDY DRUG: MLN9708

SCRI INNOVATIONS STUDY NUMBER: MM 42

FINAL PROTOCOL: 11 APRIL 2014

AMENDMENT NUMBER 3: 11 FEBRUARY 2016

VERSION 4

Page 79 of 86

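### Sites are told to report serious events over a narrower window than Section 11.4 requires, so pre-dose SAEs and late second cancers rated unrelated are not sure to be collected

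*Protocol*

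**What the plan says.** **Instructions to sites.** Section 11.1.7 has AEs of any seriousness or causality recorded on the eCRF over a period "spanning from the start of study treatment, until 30 calendar days after discontinuation or completion of study treatment". Section 11.2 gives the matching SAE period: "Serious AEs may occur at any time from the start of study treatment through 30 days after the last dose of study drug". Beyond 30 days, 11.1.7 says "only AEs, SAEs, or deaths assessed by the Investigator as treatment related are to be reported".

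**Sponsor's requirement.** Section 11.4 has SAEs go to the drug supplier's pharmacovigilance group "from the date the participant signs Informed Consent through 30 days after administration of the last dose of MLN9708". It also requires new primary malignancies to be reported "regardless of causality to study regimen, for a minimum of three years after the last dose of the investigational product". Section 7.1 sets the possible gap between consent and dosing: "Informed consent must be obtained ≤ 28 days prior to initiation of treatment".

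**Scheduled follow-up.** The notes to Appendix D give visits every three months in years 1 and 2 for patients who stop before progression. For the others: "After disease progression is documented, patients will be followed every 3 months during years 1 and 2 for survival assessment". In the Appendix D table, the pre-progression follow-up column includes adverse event evaluation. The post-progression column contains survival status and nothing else.

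**The concern.** The site window is narrower than the sponsor's window at both ends. The sponsor's safety department can forward only what it learns of, and it learns of most events from the sites.

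At the start, patients enter 45 to 120 days after an allogeneic transplant, so a serious infection between consent and first dose is plausible. Section 11.1.1 puts such an event in a separate pretreatment class. Section 11.1.8 asks for its intensity and relationship to procedures, but gives no recipient, form or time limit.

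At the end, the related-only rule conflicts directly with a duty that ignores causality. The causality guide in 11.1.8 points to *not related* when there is evidence of another cause, such as underlying disease or another treatment. A second cancer in a pretreated transplant recipient could easily be rated that way. Whether it is reported would then depend on the investigator's opinion and on whether the patient had progressed. Safety is a primary objective, and at most 38 patients are planned, so one missed second cancer matters.

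**Working it through.** The plan gives no figure to reproduce. The check compares the stated windows and does calendar arithmetic, with one month taken as 365.25/12 = 30.44 days.

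| Item | Site-facing text | Section 11.4 |
|---|---|---|
| SAE reporting opens | First dose (11.1.7, 11.2) | Signature of consent |
| SAE reporting, any causality, closes | 30 days after treatment | 30 days after last dose |
| New primary malignancy, any causality | 30 days after treatment, then related only (11.1.7) | At least 3 years after last dose |
| Scheduled contact | Years 1 and 2; survival only after progression (Appendix D) | Not stated |

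**Start.** Consent may be signed up to 28 days before dosing (7.1), so up to 28 days per patient lie inside the 11.4 window and outside the site window. Section 11.1.7 covers part of this: it has sites record pre-treatment events tied to a protocol-mandated intervention. The rest have no clear reporting instruction.

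**End, by the causality rule.** 36 months − 30 days = 36 − 30/30.44 ≈ 35.0 months. For about 35.0/36 = 97% of the required period, the site rule does not call for a malignancy rated unrelated to be reported.

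**End, by scheduled contact.** The last planned dose is Cycle 6 Day 15. With no delays, that is 5 × 28 + 14 = 154 days after Day 1, or 154/30.44 ≈ 5.1 months. The requirement then runs to 5.1 + 36 ≈ 41.1 months after Day 1. Appendix D does not say when its years 1 and 2 begin, so the shortfall is a range:

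- From end of treatment, as 7.4 does for response assessments (two years after completing maintenance), taking last dose and end of treatment as the same point: 36 − 24 = 12 months.
- From Day 1: 41.1 − 24 ≈ 17 months.
- With a fresh two-year clock at progression: a patient who progresses 15 months after the last dose has contacts until 15 + 24 = 39 months, past 36. The calendar gap is nil, but those contacts ask only about survival.

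**Against the planned duration.** Section 5.2 plans about 3 years, or 36 months, from first patient enrolled to last patient out. A patient who completes treatment reaches the end of the 11.4 period about 41 months after Day 1. That is about 5 months beyond the planned study even for the first patient enrolled.

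**The case against.** A reader might infer that these events are never collected. The documents do not support that, because several routes exist:

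- Section 11.3.7 is addressed to sites. It makes a new primary cancer arising after inclusion an AE, generally a serious one, and states no end date.
- Appendix D schedules adverse event evaluation at follow-up visits before progression.
- Section 11.1.7 records pre-dose events tied to a protocol-mandated intervention, and 11.1.8 presupposes that serious pretreatment events come to the investigator's attention.
- Treatment-related events stay reportable without an end date.
- Section 11.4 is part of the protocol that investigators sign. Its malignancy sentence does not confine the duty to sponsor staff.

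Two other strong readings also fail. One is that no month after progression captures a malignancy: progression ends treatment, but any-causality recording continues for 30 days after treatment stops, and related cancers remain reportable after that. The other is that every one of the 38 patients has at least 12 months without contact: the start of the follow-up clock is not stated, and 38 is a ceiling.

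The effect on the analysis is also limited. Pre-dose events fall outside the treatment-emergent definition in Protocol 10.4.3 and SAP section 7. None of the SAP's 14 tables counts new malignancies.

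All of this stands, but it does not remove the contradiction. Section 11.3.7 makes a new cancer an AE, which places it under the related-only rule in 11.1.7, and it states no exemption or three-year period. The follow-up adverse event evaluation falls under the same rule and appears only in the pre-progression column.

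**Conclusion.** The point holds as an internal contradiction that leaves collection uncertain. Collection is not assured for three groups:

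- serious events in the up to 28 days before first dose that are unrelated to a protocol-mandated intervention;
- new malignancies rated unrelated more than 30 days after treatment, especially after progression;
- malignancies arising after scheduled follow-up ends, a shortfall of about 12 to 17 months depending on the clock, and possibly nil where a post-progression clock starts late.

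The wording conflict is certain. How many events would be missed cannot be said from the documents. The month counts assume six cycles without delay.

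The effect is on the completeness of safety reporting, mainly to the drug supplier. It does not touch PFS, OS or sample size, and it is not a defect of the treatment-emergent tables. One qualification: the treatment-emergent definition has no closing date, so a late cancer that was entered as an AE could appear in the general safety tables. No planned analysis depends on a malignancy count. The change is worth making because it is cheap and because safety is a primary objective.

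**What to change.** 1. In 11.1.7 and 11.2, start SAE reporting at signature of consent.
2. Add to the 30-day sentence in 11.1.7: *except new primary malignancies, which are reported regardless of causality for the period required in Section 11.4*. Cross-refer to it from 11.3.7.
3. In Appendix D, add a new-primary-malignancy item to both follow-up columns, and state when years 1 and 2 begin in each.
4. Clarify the malignancy sentence in 11.4, which counts three years from the last dose and also says the period starts at the first dose.
5. Reconcile the three-year requirement with the two-year follow-up and with the planned duration of about 3 years in 5.2. A telephone or record check at 36 months after the last dose falls about 41 months after Day 1. Either the stated duration changes, or this reporting is handled outside scheduled follow-up.

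Items 1 to 4 cost protocol and eCRF wording, a few more SAE reports and one added question at existing contacts. Item 5 costs more: a possible later final contact, and an extension of the study if the check is made within it.
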